#### (iv) Design

This double-blind, placebo controlled, randomized clinical trial will enroll BrCA patients seen at the Emory Breast Centers (Winship Cancer Institute of Emory University and Emory University Hospital Midtown) or in the community for XRT who were previously treated with chemotherapy. These patients will be approached for enrollment on this therapeutic study during the first three weeks of receiving radiation therapy or one to three months post XRT.

In patients previously treated with chemotherapy, we will administer placebo or Meriva daily for approximately 6 weeks, beginning immediately after the completion of XRT or up to 3 months post-XRT. Patients will be randomized to placebo or Meriva-500 (500 mg PO BID) using a computerized system under the control of Emory Pharmacy. Randomization will occur in blocks of 10. Meriva-500 will be obtained from Thorne Research. Blood will be drawn at baseline and at the first follow-up appointment to determine NF-kB DNA-binding in peripheral blood mononuclear cells, expression of NF-kB regulated genes, and plasma cytokine concentrations. The final study visit will occur during the 6 week treatment period. Study Coordinator will make an effort to coincide the follow up visit and six week post-radiation follow up visit. Because placebo or Meriva is being given after XRT is complete, it is unlikely to alter the efficacy of the XRT or enhance side effects of XRT.

Thirty patients will be enrolled per arm. NF-kB DNA-binding, downstream mediators of NF-kB activity and microarray analysis of NF-kB regulated genes will be used to determine NF-kB pathway activation. If any of these measures of NF-kB DNA binding activity (the primary outcome variables)

**Patients will receive daily Meriva treatment for approximately 6 weeks beginning immediately after radiation therapy (XRT) or up to 3 months post-XRT. Peripheral blood will be drawn during the last week of XRT and again after 6 weeks of Meriva (or Placebo) for assessment of NF-kB pathway activation.**

decrease to the mean level of non-chemotherapy treated women who receive XRT, the 500 mg BID dose level will be considered successful.

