#### (vi) Observations and measurements

Based on work performed in prior studies, we do not anticipate biomarker responses that would suggest adverse reactions to Meriva (1-4). We will therefore not collect blood samples during the 6 week treatment with Meriva to monitor adverse biomarker responses. Research blood will be collected at baseline during the last week of XRT or up to three months post XRT and at the conclusion of the 6 weeks treatment with Meriva. Patients will be interviewed weekly by phone to ensure they are not experiencing side effects previously described for curcumin, including nausea and diarrhea. If they do report worsening of these symptoms compared to before they started Meriva, they will be asked to immediately discontinue taking Meriva and come to the clinic for full physical evaluation. In the case that a patient experiences adverse side effects and stops taking Meriva, self-report information and blood samples will still be collected at the early termination visit.

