### Outcome Measures

The primary outcome to be measured will be the change in NF-kB DNA binding and its downstream mediators (plasma concentrations of TNF-alpha, sTNFR2, IL-1ra, IL-6 and CRP) after six weeks of treatment with daily placebo or Meriva. The secondary endpoint will be the change in fatigue from baseline to six weeks after treatment with Meriva or placebo. . Microarray analysis will also be performed before and after treatment to look at the expression of NF-kB response genes: **Primary Hypothesis: Patients responsive to Meriva will have decreased NF-kB DNA binding, decreased activation of NF-kB responsive genes and decreased downstream mediators of NF-kB pathway activation.**

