### Analytical Plan

Power analysis: Based on a preliminary data, the mean change of NF-kB DNA binding from baseline among patients who underwent six weeks XRT was 8.2 ng NF-kB per assay well (SD = 9.0). We hypothesize that in this study the patients in the placebo group will have the similar response as in the preliminary data, and patients who receive Meriva, the mean change of NF-kB DNA-binding level from baseline to 6 weeks post XRT is 0.0 with a reduced SD of 4.5. Based on alpha of 0.05 and a n = 11 per group, we will have 82% power to detect the above hypothesized difference by one-sided two-sample t test. We believe such a difference is clinically meaningful and is well within the range of differences observed in chemotherapy vs. no chemotherapy patients and fatigued vs. non-fatigued patients.

Statistical analysis plan: Primary objectives: the mean changes of NF-kB DNA binding from baseline to Week 6 will be compared between two groups using two-sample t test. The change of plasma concentration of NF-kB downstream mediators from baseline will be compared between two groups using two-sample t-test/Wilcox sum rank test for continuous measures and using Chi-square test/Fisher's exact test for categorical measures. Secondary objectives: The change of MFI over time in two groups will be compared by the GEE model.

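### The primary endpoint visit is timed by two clocks, days on drug and time since radiation, which agree only when drug starts as radiation ends

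*Combined protocol and SAP*

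**What the plan says.** All references are to the combined protocol and SAP.

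**Treatment clock.**
- Outcome Measures defines the primary change "after six weeks of treatment with daily placebo or Meriva".
- Section (vi) Observations and measurements takes the second research sample "at the conclusion of the 6 weeks treatment with Meriva".
- The bold text in (iv) Design likewise draws the second sample once six weeks of study drug have been given.
- The Visit III description places that visit in the last week of study treatment.
- The Curcumin Study Checklist puts Visit III after the calls for treatment weeks 1 to 5, with drug and diaries returned.

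**Radiation clock.**
- Section (iv) Design adds: "Study Coordinator will make an effort to coincide the follow up visit and six week post-radiation follow up visit".
- The power paragraph of the Analytical Plan assumes that the Meriva-arm mean change "from baseline to 6 weeks post XRT is 0.0".

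**Not tied to either clock.**
- Section (iv) Design says "The final study visit will occur during the 6 week treatment period", with no day or window.
- The analysis paragraph of the Analytical Plan compares changes to Week 6 without saying what week zero is.

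**Start of drug.** Treatment is given "daily for approximately 6 weeks, beginning immediately after the completion of XRT or up to 3 months post-XRT". Patients are approached "during the first three weeks of receiving radiation therapy or one to three months post XRT". The baseline visit may itself fall up to three months after radiation, and dosing starts on the Monday after dispensing.

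**The concern.** A visit six weeks after radiation and a visit after six weeks on drug are the same visit only if drug starts when radiation ends. The plan allows a lag of up to three months and makes recruitment at one to three months after radiation a formal route. The pairing instruction makes no exception for patients with a lag.

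A coordinator who followed it for such a patient would take the primary sample early. If the drug effect builds with time on treatment, early samples in the active arm pull the treatment difference toward zero. The planned two-sample t test takes no account of days on drug, so the analysis would neither show nor correct this. Start lag is largely fixed by the time of randomization and should be balanced between arms in expectation. The risk is therefore loss of sensitivity, not a false positive.

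**Working it through.** **1. The plan's own power figure.** Inputs from the Analytical Plan: mean change 8.2 (SD 9.0) on placebo and 0.0 (SD 4.5) on Meriva, n = 11 per group, one-sided alpha 0.05.

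- Standard error = √(9.0²/11 + 4.5²/11) = √(7.364 + 1.841) = 3.034.
- Noncentrality = 8.2 / 3.034 = 2.70.
- Satterthwaite df = (7.364 + 1.841)² / (7.364²/10 + 1.841²/10) = 14.7.
- Power from the noncentral t = 82.4%.

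The stated 82% is reproduced. Start lag does not enter the calculation, so the timing conflict does not make the figure wrong.

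**2. What the two clocks imply.** Let L be the weeks from the end of radiation to first dose.

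- Weeks on drug at a visit held six weeks after radiation = 6 − L.
- Weeks since radiation at a visit held after six weeks on drug = 6 + L.

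One month is taken as 4.345 weeks and three months as 13.04 weeks.

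| Start lag L | Weeks on drug if paired | Weeks since radiation if counted from first dose |
|---|---|---|
| 0 | 6 | 6 |
| 1 week | 5 | 7 |
| 2 weeks | 4 | 8 |
| 1 month | 1.7 | 10.3 |
| 6 weeks | cannot be paired | 12 |
| 3 months | cannot be paired | 19 |

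At 1 month, 6 − 4.345 = 1.655 weeks, and 1.655 / 6 = 28% of the planned exposure.

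**3. Who can be affected.** At L = 0 the clocks agree. At L of six weeks or more, the radiation follow-up has come by the day of first dose or earlier. It cannot serve as a final visit, so there is nothing to pair. Exposure can be shortened only for 0 < L < 6 weeks, and then only if pairing is put ahead of the treatment clock.

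**4. Size of the dilution.** This needs the share of patients with 0 < L < 6, how many of them would be paired, and how the effect depends on time on drug. The documents give none of these, so no figure for lost power is offered.

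**The case against.** The strongest reply is that the plan already ties the visit to treatment. The bold Design text, section (vi), the Visit III description, Outcome Measures and the checklist all do so. A visit in the last treatment week does fall within the treatment period, so the sentence in (iv) Design can be read consistently with them, and it keeps the patient on drug. The pairing is an effort and does not override the Visit III description. Pairing a patient who started at one month would mean closing her out less than two weeks after first dose and skipping most of the scheduled calls, which staff are unlikely to do. Patients approached after radiation must also complete screening and baseline first, so few of them would start before week six. The radiation wording in the power text can be read as a loose label carried over from a radiation cohort.

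Most of this stands, and it limits the point to a possibility. It does not remove the conflict. The pairing sentence has no exception for a lag, the radiation anchor recurs in the power text, and no section gives a visit window in days from first dose. Lags of one or two weeks, where pairing looks harmless, are the easiest to let through.

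**Conclusion.** The plan gives inconsistent timing for its primary measurement, and the passages should be reconciled. The practical risk is limited to patients who start after the end of radiation but before six weeks and are paired anyway. They would have 5, 4 or about 1.7 weeks on drug at lags of 1 week, 2 weeks and 1 month. The consequence would be some dilution of the treatment difference, if the effect grows with exposure; its size cannot be estimated from the documents.

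A reader might infer that late starters will be measured after little or no treatment. The documents do not support that: most of the text places the visit at the end of treatment, pairing is not mandatory, and a start at or beyond six weeks cannot be paired, so no zero-exposure measurement arises. Nor do they support the inference that the power statement is wrong on this account.

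This is a cheap improvement of minor severity.

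**What to change.** - In (iv) Design and the Analytical Plan, count the endpoint visit from first dose, with a stated window in days, to agree with section (vi), the Visit III description and Outcome Measures. State that Week 6 is counted from first dose.
- Restrict the pairing sentence to patients whose radiation follow-up falls inside that window.
- Record days on drug at the final draw, so that actual exposure can be reported by arm.

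The cost is protocol wording and one derived data item. Some patients lose a combined visit. Time since radiation at the final draw will then vary, from about 6 to 19 weeks over the permitted start lags; that already follows from the start window, and randomization should balance it in expectation. This concerns measurement timing only, and no change to dose or treatment length is proposed.

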**(v) Dosing**

The 500 mg BID dose of Meriva that will be used in this protocol was selected after consulting with [name], DVM, Head of Business Development at Indena S.p.A (Milan, Italy) and [name], Chief Scientific Advisor, Indena S.p.A (Milan, Italy). The dose proposed for use here is similar to doses used in other studies investigating Meriva (1-4). For example, the single dose selection is also supported by a recent study by Cuomo and colleagues showing that 200-300 mg of curcumin as Meriva (i.e. a single Meriva dose of 1000-1500 mg) resulted in 29-fold higher for Meriva than for its corresponding unformulated (non phosphatidylcholine) curcuminoid mixture. In terms of the length of Meriva treatment, 6 weeks was chosen because it is the period of time over which we have observed a significant increase in NF-kB pathway activity related to fatigue symptoms (31).

We propose to increase the dose of Meriva 500 administered to patients randomized to the active arm of the study from 1 to 2g total per day (500mg to 1g BID, respectively). This dose increase will be implemented 1) after 10 patients have completed the protocol (5 active and 5 placebo), 2) if no statistically significant differences are noted at the primary study endpoint (peripheral blood mononuclear cell NF-kB DNA-binding) between patients randomized to the active arm and patients randomized to the placebo arm, and 3) no dose-limiting side effects have been encountered. Dose-limiting side effects are considered to be a Grade 3 (Based on NCI Common Terminology Criteria for Adverse Events) or higher adverse event that is deemed to be probably related to the drug.

The change to 2g/d dose is supported by Mantovani and colleagues who reported beneficial effects of 2g/d Meriva on inflammatory biomarkers in cancer patients taking Meriva for 1 month (50). Also supporting this modification is a trial comparing the analgesic effects of 1.5g vs. 2g Meriva in a mixed patient group with different sources of pain (e.g. arthritis, neuropathy, recurrent headaches) (51). In general the results of this study suggest that Meriva at 2g/d may be more efficacious than Meriva at 1 g/d. Finally, a recent paper by Drobic and colleagues found that 2g/d decreased inflammatory markers and muscular damage in healthy men undergoing intense physical exercise (52). No tolerability issues were noted in either of these studies except for mild nausea and heartburn in the report by Di Pierro et al. (51), which was attributed to the bulk of capsules consumed and not the content of the capsules.

Of note, because of difficulty obtaining enough cells from the blood of the first 10 subjects who completed the study, we were unable to measure peripheral blood NF-kB DNA binding. Therefore, because we could not statistically compare NF-kB DNA binding between groups, the Meriva dose of 1 g per day was maintained without an increase (as per protocol). In addition, statistical consultation based on IL-6 values in the first 10 completed subjects suggested that continuing enrollment at the Meriva 1 mg dose would give sufficient power (>0.80) to detect a difference in this NF-kB-related inflammatory endpoint at study completion or after enrollment of at least 40 subjects. Similar findings were observed with fatigue. For these reasons, the Meriva dose will be continued at 1mg per day for the entirety of the study for all subjects.

Although a maximum tolerated dose (MTD) for Meriva has not yet been identified in any population, most published studies have tested doses of either 1 or 2 g/d Meriva (containing 200-400 mg curcuminoids) (53). By extrapolation of pharmacokinetic data (54,55), 2 g/d Meriva (containing 400 mg curcuminoids) dose may be bioequivalent to either 4 or 12 g/d non-complexed curcuminoids, corresponding to the middle range of curcuminoid doses previously tested in humans. Of note, the highest oral dose of Meriva being tested in humans is 4 g/d Meriva (containing 800 mg curcuminoids) (NCT01859858). However this study is ongoing, and information related to effectiveness and adverse events (AEs) is not available. All reported AEs for Meriva up to 2 g/d have been limited to grade 1 or 2 gastrointestinal symptoms and chronic toxicity studies in rats suggest that a human equivalent dose of 24 g/d Meriva is safe in humans (56).

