**IRB#00055328**

Curcumin Study Checklist										
	CLINIC VISIT	CLINIC VISIT	CLINIC VISIT						CLINIC VISIT	CLINIC VISIT
Procedure	Initial Meeting	Visit I Screening	Visit II Baseline	Tx wk 1 Call	Tx wk 2 Call	Tx wk 3 Call	Tx wk 4 Call	Tx wk 5 Call	Visit III	Early Termination
Curcumin ICF for review	x									
Curcumin Consent		x								
Inclusion Criteria		x								
Demo Sheet		x								
Physician/NP Evaluation		x							x	
Physical Examination										x
Urinalysis		x								
Serum quantitative pregnancy		x								
CBC w/diff		x							x	x
Review labs for infection and anemia		x							x	x
Blood draw for research: 4 purple tops and 1 tempus			**						**	**
Randomize/dispense meds			***							
Patient reimbursement		x	x						x	x
Phone Interview				*	*	*	*	*		
Meds returned/counted									x	x
Meds diary returned									x	x
Concomitant Medications reviewed		x	x	x	x	x	x	x	x	x
Adverse Events Reviewed				x	x	x	x	x	x	x
Ultrasound scan and photographs			x						x	
Fatigue Level		x	x						x	x
Pain Level		x	x						x	x
Mediterranean Diet Survey			x							
GLTEQ			x						x	x
MFI 20			x						x	x
PSS			x						x	x
IDS-SR		x	x						x	x
PSQI			x						x	x
PROMIS		x	x						x	x
* Weekly phone interviews for Adverse Event Assessment/ Medication Compliance. If indicated, stop medications and come in for physical exam.										
** Plasma analysis of inflammatory markers, PBMC analysis of NF-kB DNA binding, and gene expression.										
*** Medication dispensed during treatment check by physician or nurse practitioner. Medication to begin the following Monday after medications are dispensed.										
v. 12/19/2017										

Blood samples will be drawn at the same time of day between 9:00-11:00 am (to reduce potential circadian effects) under sterile conditions at each of these visits. Whole blood for plasma, buffy coat, and peripheral blood mononuclear cells (PBMCs) will be collected into EDTA vacutainer tubes. Two tubes will be stored at 4°C for less than 45 minutes, after which plasma and buffy coat will be separated by centrifugation at 1000 x g for 10 minutes at 4°C, aliquoted into siliconized polypropylene tubes and stored at -80°C until assayed. Two tubes will be kept at room temperature for less than 45 minutes, after which plasma will be replaced

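### The planned t test on NF-kB change would drop any patient with only one usable sample, on an assay already known to fail; a model using all samples is a cheap safeguard, with a conditional gain

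*Combined protocol and SAP*

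**What the plan says.** - **Assay failure.** The Dosing section attributes the missing NF-kB data to "difficulty obtaining enough cells from the blood of the first 10 subjects who completed the study, we were unable to measure" binding in peripheral blood. It does not say which visit's sample failed, whether anyone had one usable sample, or whether the problem continued.
- **Sampling.** Research blood is drawn at baseline and at the end of about six weeks of treatment. The study checklist lists, for both draws and for early termination, "Plasma analysis of inflammatory markers, PBMC analysis of NF-kB DNA binding, and gene expression".
- **Test.** The Analytical Plan states that "the mean changes of NF-kB DNA binding from baseline to Week 6 will be compared between two groups using two-sample t test". A repeated-measures method (GEE) is named for the fatigue score only.
- **Power.** "Based on alpha of 0.05 and a n = 11 per group, we will have 82% power" "by one-sided two-sample t test". Placebo is given a mean change of 8.2 with SD 9.0; for Meriva the mean change "from baseline to 6 weeks post XRT is 0.0 with a reduced SD of 4.5".
- **Size.** The inclusion criteria and Design sections plan 60 patients, 30 per arm.

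The Analytical Plan has no allowance for assay yield and no rule for a missing NF-kB sample.

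**The concern.** A change score exists only if both assays succeed. With a per-sample yield q and independent failures, about q² of patients form a pair, so at 70% yield roughly half the patients leave the comparison. Some of them would have a valid Week-6 value. Randomisation makes the arms comparable at baseline on average, so that value bears on the treatment effect without its own baseline. Neither the change-score test nor an ANCOVA restricted to complete pairs can use it.

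At stake is precision on the only endpoint with a formal power calculation, and an analysis set that would otherwise be settled after the pattern of failures is known.

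**Working it through.** **1. Reproduce the stated power.** Difference 8.2, SDs 9.0 and 4.5, 11 per group, one-sided 0.05. Standard error = √(81/11 + 20.25/11) = √9.205 = 3.034; noncentrality = 8.2/3.034 = 2.70. The unequal-variance noncentral t gives 82.4%, which matches the stated 82%.

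**2. Margin for lost pairs.** The same calculation gives 99.7% at 30 pairs per arm, 99.1% at 25 and 92.0% at 15. Power falls below 82% only under 11 pairs. From 25 per arm, with independent failures, that needs a per-sample failure rate above 1 − √(11/25) = 34%.

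**3. Assumptions for the comparison** (not in the documents unless stated):
- n = 25 per arm: 60 less the first 10, split 5 and 5 as the Dosing section foresaw, with no other dropout.
- Yield q of 60%, 70% or 80%; failures independent between visits and unrelated to the values.
- Correlation ρ = 0.5. Visit SD = SD of change/√(2(1 − ρ)), which at ρ = 0.5 equals the SD of change.
- One-sided 0.05, as in the power calculation. The analysis text itself does not state sidedness.

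Per arm, pairs m = 25q² = 9, 12.25, 16. Week-6-only patients s = 25q(1 − q) = 6, 5.25, 4.

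**4. Variance of the treatment difference.** Let S = 81 + 20.25 = 101.25 with the plan's SDs, or 81 + 81 = 162 with SD 9.0 in both arms (a sensitivity assumption, not a figure from the plan).
- Change-score test: S/m.
- ANCOVA on pairs: S(1 − ρ²)/m.
- All samples, common baseline mean: S/(m/(1 − ρ²) + s). In this symmetric case baseline-only patients cancel out, so the gain comes from Week-6-only patients.

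Example, q = 60%, plan's SDs: ANCOVA 101.25 × 0.75/9 = 8.44; all samples 101.25/(12 + 6) = 5.63.

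Power is noncentral t for the planned test and Φ(8.2/√variance − 1.645) for the other two.

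| SDs | Yield | Planned t test | ANCOVA, pairs | All samples | Sample recovery alone |
|---|---|---|---|---|---|
| 9.0 / 4.5 | 60% | 74.4% | 88.1% | 96.5% | 8 points |
| 9.0 / 4.5 | 70% | 86.2% | 95.0% | 98.4% | 3 points |
| 9.0 / 4.5 | 80% | 93.5% | 98.3% | 99.3% | 1 point |
| 9.0 / 9.0 | 60% | 58.1% | 72.1% | 86.2% | 14 points |
| 9.0 / 9.0 | 70% | 70.6% | 83.1% | 91.1% | 8 points |
| 9.0 / 9.0 | 80% | 80.9% | 90.8% | 94.5% | 4 points |

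The normal approximation slightly flatters the last two methods. On that scale the planned test with the plan's SDs would read 78.8%, 88.6% and 94.7%.

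**5. Sensitivity.**
- *Correlation 0.3 to 0.7, q = 60%.* Plan's SDs: ANCOVA 92% to 84%, all samples 99% to 92%. SD 9.0 in both arms: 77% to 67%, and 92% to 78%.
- *Equal baseline SDs.* Step 3 implies a smaller baseline SD on Meriva, which randomisation would not produce. Take visit SD 9.0 throughout and a Meriva correlation of 1 − 20.25/(2 × 81) = 0.875, which keeps its SD of change at 4.5. Inverting the information matrix for the common-baseline model gives variances of 9.49, 6.97 and 5.34 on pairs only (84.5%, 92.8%, 97.2%) and 6.74, 5.52 and 4.62 on all samples (93.5%, 96.8%, 98.5%). The picture is unchanged.
- *Clustered failures, within-patient correlation of failure 0.5, q = 60%.* Pairs = 25(0.36 + 0.5 × 0.24) = 12; Week-6-only = 15 − 12 = 3. Plan's SDs: 85.5%, 94.7% and 97.2%. SD 9.0 in both arms: 69.8%, 82.4% and 87.8%. Recovery falls to about 2.5 and 5 points.
- *Both samples always fail together.* s = 0, so the all-samples variance equals the ANCOVA variance and recovery is nil.

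**The case against.** Most of the case on the other side stands as a limit on size.

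- A reader might infer that patients with one good sample have already been discarded. The documents describe no such patient. They report that the assay could not be done in the first 10 completers as a group; the loss of half-complete patients follows from the chosen test.
- That group-wide failure, with the same tubes planned at both visits, fits a shared cause at least as well as independent failures. If both samples fail together, or failure stays near-total, recovering single samples rescues nothing.
- A reader might infer that the trial is underpowered on this account. With the plan's own SDs, losing all of the first 10 leaves about 99%, and the planned test still exceeds 82% at 70% and 80% yield. The less comfortable figures need SD 9.0 in both arms.
- Much of the gap between the planned test and the all-samples model is ordinary baseline adjustment, which ANCOVA would also deliver.
- A reader might suspect bias because cell yield depends on immune state. Nothing in the documents supports that. If yield depended on the unobserved NF-kB value, the proposed model would be biased too.

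What survives is narrower: a known failure mode, a test that needs both samples, no stated rule, and a remedy that adds no data collection.

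**Conclusion.** The point holds in a conditional form. Under the assumptions in step 3, using all samples adds about 8, 3 and 1 points of power over complete-pair ANCOVA at 60%, 70% and 80% yield with the plan's SDs, or about 14, 8 and 4 points with SD 9.0 in both arms. Against the planned t test the total gain is larger, roughly 22, 12 and 6 points with the plan's SDs, but that includes baseline adjustment and a small effect of the normal approximation. Yield, correlation and failure pattern are all assumed. The planned test drops below its stated 82% only under 11 pairs per arm. Priority lies between optional and recommended: the harm is unproven, but the change is cheap and closes a gap that the sponsor already knows about.

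**What to change.** In the Analytical Plan, make the NF-kB analysis one longitudinal model on every available baseline and Week-6 value:
- common baseline mean, with separate Week-6 means by arm;
- unstructured covariance allowed to differ by arm, because the power calculation assumes unequal SDs;
- restricted maximum likelihood with a small-sample degrees-of-freedom method such as Kenward-Roger;
- the Week-6 difference as the treatment effect. Under randomisation this targets the same quantity as the difference in mean change.

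Keep the complete-pair t test as a sensitivity analysis. Report usable samples by visit and arm. Fix this before unblinding.

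Cost: SAP wording and one standard model, with no added patients, visits or samples. The downside is reliance on missing-at-random at modest sample size, with arm-specific covariances estimated from few pairs. The t test gives a check on the model form, though it also excludes incomplete patients and does not test that assumption.

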Curcumin, a known inhibitor of NF-kB, has been shown to decrease NF-kB activation in human participants. In a recent study, 8 grams of curcumin by mouth daily for 8 weeks was well tolerated in patients with pancreatic cancer and other pre-malignant conditions with no associated toxicities (6, 8). Although there is concern over the body's absorption of curcumin, the bioavailability of curcumin in the study of pancreatic cancer patients was shown, with peak drug levels at 22 to 41ng/mL that remained relatively constant over the first 4 weeks of treatment with 8 grams of curcumin daily (8). Clinical trials with daily dosages of 1,125 to 2,500mg have also confirmed the safety of curcumin and also shown its ability to decrease inflammation in patients with rheumatoid arthritis and in post-operative patients (6, 33, 34). In vivo murine models of chronic fatigue syndrome have also shown that curcumin may also alleviate symptoms of fatigue (35). While these studies are promising, very little is known about the capacity of Meriva to inhibit NF-kB in women treated for BrCA. We hypothesize that oral Meriva, a known inhibitor of NF-kB, may be used to decrease levels of NF-kB activity in BrCA patients previously treated with chemotherapy who go on to receive radiotherapy (XRT), a carefully chosen group of patients at particular risk for high levels of NF-kB DNA binding (a direct measure of NF-kB pathway activity).

We have chosen to administer oral Meriva, 500mg BID, in our patient population based on the above data. Meriva-500 is a curcumin formulation that also contains phosphatidylcholine, derived from soy that has been shown to aid in absorption of curcumin (9), permitting a lower overall dose of curcumin. Of note, 1000 mg Meriva contains 200 mg curcuminoids (>90% curcumin).

By decreasing activity of NF-kB, fatigue may improve in BrCA patients taking Meriva. Results from this study will contribute to the limited research available on the capacity of curcumin treatment, including Meriva, to inhibit NF-kB and its downstream mediators in vivo as well as symptoms of fatigue associated with excessive NF-kB pathway activity in BRCA patients.

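### Section (v) Dosing gives the Meriva dose for the rest of the study as 1 mg per day, a factor of 1,000 from the 1 g per day (500 mg BID) stated elsewhere

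*Combined protocol and SAP*

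**What the plan says.** Section (i) Background and objectives introduces the regimen: "We have chosen to administer oral Meriva, 500mg BID, in our patient population based on the above data". It adds the content of the product: "1000 mg Meriva contains 200 mg curcuminoids".

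Section (iv) Design repeats the regimen in the randomization sentence, "Patients will be randomized to placebo or Meriva-500 (500 mg PO BID", and again in the success rule, under which "the 500 mg BID dose level will be considered successful" if a pathway measure falls to a reference level.

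Section (v) Dosing opens with the same figure: "The 500 mg BID dose of Meriva that will be used in this protocol". Its second paragraph sets out a conditional increase after 10 completers and equates 500 mg BID with a total of 1 g per day, and 1 g BID with 2 g per day.

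A later paragraph of section (v) reports that NF-kB DNA binding could not be measured in the first 10 completers. It then makes three dose statements in succession:

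- The outcome of the escalation question: "the Meriva dose of 1 g per day was maintained without an increase (as per protocol".
- The power argument based on IL-6: "continuing enrollment at the Meriva 1 mg dose would give sufficient power (>0.80".
- The concluding sentence: "the Meriva dose will be continued at 1mg per day for the entirety of the study for all subjects".

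The closing paragraph of section (v) discusses doses tested elsewhere and tolerability. It sets no dose for this trial.

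**The concern.** Within one paragraph, the study-drug dose is given as 1 g and then twice as 1 mg. The verbs in that paragraph describe a single unchanged dose, so the two figures cannot both be correct. The final sentence is not background: it settles the escalation question and states the dose for the remainder of the trial.

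Three things are at stake.

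- **The written dose.** Someone who goes to section (v) for the dose that applies after the first 10 completers finds 1 mg per day as the last figure set for this trial.
- **The success rule.** Section (iv) words the rule for 500 mg BID. It does not describe a 1 mg regimen.
- **The recorded reason for not escalating.** The IL-6 argument uses data from the first 10 completers, whose active-arm dose the same paragraph gives as 1 g per day, yet it claims power at a 1 mg dose. As written, the data and the claim refer to different doses.

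**Working it through.** **Dose statements side by side**

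| Place | Dose as stated | Daily total |
|---|---|---|
| (i) Background and objectives | 500 mg BID | 1,000 mg |
| (iv) Design, randomization sentence | 500 mg BID | 1,000 mg |
| (iv) Design, success rule | 500 mg BID | 1,000 mg |
| (v) Dosing, opening sentence | 500 mg BID | 1,000 mg |
| (v) Dosing, escalation paragraph, starting dose | 1 g per day, equated with 500 mg BID | 1,000 mg |
| (v) Dosing, dose kept after 10 completers | 1 g per day | 1,000 mg |
| (v) Dosing, IL-6 power sentence | 1 mg (no frequency given) | 1 mg if daily |
| (v) Dosing, concluding sentence | 1 mg per day | 1 mg |

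The count is six statements against two.

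**The protocol's own conversion.** 500 mg × 2 = 1,000 mg = 1 g per day. This reproduces the equivalence given in the escalation paragraph.

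**Size of the discrepancy**

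- Ratio of daily doses: 1,000 mg / 1 mg = 1,000.
- Curcuminoid fraction from section (i): 200 / 1,000 = 0.20. Daily curcuminoids are 1,000 mg × 0.20 = 200 mg, against 1 mg × 0.20 = 0.2 mg.
- Total Meriva over about 6 weeks, taken as 42 days: 42 × 1 g = 42 g, against 42 × 1 mg = 42 mg.

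The last two lines restate the same factor of 1,000 in other units. They are not separate effects.

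**Does it reach the power calculation?** The Analytical Plan takes mean changes of 8.2 (SD 9.0) and 0.0 (SD 4.5), 11 patients per group, and a one-sided t test at 0.05, and states 82% power.

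- Standard error: √(9.0²/11 + 4.5²/11) = √(101.25/11) = 3.034.
- Noncentrality: 8.2 / 3.034 = 2.70.
- With Satterthwaite degrees of freedom of 14.7, the noncentral t distribution gives 82.4% power, in agreement with the plan.

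No dose enters this calculation, so the discrepancy leaves it unchanged. The IL-6 power claim in section (v) gives neither an effect size nor an SD, so it cannot be recomputed at either dose.

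**The case against.** The strongest reply is that this is a slip of unit that nobody would act on. The paragraph speaks of a dose kept and continued, so it does not announce a change. The product is named Meriva-500, the regimen is stated clearly in the randomization sentence and at the start of section (v), and nothing describes a 1 mg supply. The conflicts with the success rule and with the IL-6 sentence are the same discrepancy seen from other places. No statistical quantity moves.

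Much of this stands. The documents give no sign that any patient received a different dose, and the consequences listed should not be counted as separate errors. This is an inconsistency of units; no calculation in the plan fails. On the IL-6 point, the escalation rule envisages five active and five placebo patients among the first 10, so the 1 g per day can describe only the active-arm patients.

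What does not stand is the inference that the text can be left alone. The 1 mg figure appears in two separate sentences with different spacing, so a single text-extraction fault is unlikely. It is in current body text, not in a change log. That a careful reader might guess the intention is not a reason to leave two doses 1,000-fold apart in the section that sets the dose.

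**Conclusion.** The concern holds. Section (v) Dosing states the daily Meriva dose both as 1 g and as 1 mg, and its concluding sentence uses the latter, against six statements in sections (i), (iv) and (v) at 1 g per day or 500 mg BID. The discrepancy is exactly 1,000-fold: 200 mg against 0.2 mg of curcuminoids per day at the protocol's stated content. It must be fixed because it concerns the investigational dose in the section that sets it.

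The conclusion rests only on the text and on unit conversion. The one approximation is 42 days for a treatment period described as about 6 weeks, and it affects only the cumulative totals. The conclusion does not depend on any patient having been dosed differently, and the 82% power in the Analytical Plan is untouched. No view is taken on which dose is right.

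**What to change.** Reconcile sections (i), (iv) and (v) so that one daily dose is stated consistently, always with its unit and frequency. This includes the IL-6 power sentence and the concluding sentence of that paragraph. The sponsor should confirm the dose from its own records and not infer it from the count of statements above.

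In the same edit, add a short note on the status of the escalation paragraph in section (v). It still describes the increase as something to come, while the later paragraph closes the question without one. This second item is editorial.

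The cost is a few words of text in a protocol amendment. No analysis, endpoint or sample size changes.
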